6.3.5. Visit 11 (28 to 42 Days After Visit 10), Postbooster Blood Draw

- Ensure that the subject continues to be eligible for the study, and continues to comply with contraception requirements detailed in [Section 4.5](#).
- Ensure that the subject continues to meet none of the withdrawal criteria as described in [Section 6.5](#) and none of the temporary delay of blood draw criteria as described in [Section 4.4](#).
- Collect the subject's e-diary.
- Review the subject's e-diary data since the previous visit and follow up on any ongoing reactogenicity or use of antipyretic medication.
- Complete the Study Visit/Telephone Contact AE Checklist to:
 - Inquire whether the subject had any newly diagnosed chronic medical conditions since the last visit. Inquire whether the subject had any of the following related to an AE since the last visit: hospitalizations, visits to other medical facilities, medication use, or missed days of school or work. Please refer to the SRM for additional details.
 - Inquire about neuroinflammatory and autoimmune conditions, such as transverse myelitis, uveitis, optic neuritis, and multiple sclerosis. Please refer to the SRM for additional details.
- Record AEs as described in the AE Reporting Requirements section ([Section 8](#)) and the [Schedule of Activities](#).
- Review AEs that were ongoing since the previous visit and record their end dates or confirm that they are still continuing.

- Record nonstudy vaccinations as described in the Concomitant Treatment(s) section ([Section 5.11](#)).
- Record concomitant medications used to treat AEs as described in the Concomitant Treatment(s) section ([Section 5.11](#)).
- Provide the parent(s)/legal guardian or the subject with a memory aid. Instruct the subject to use the memory aid between Visits 11 and 12 to remind him or her to review any significant illnesses, hospitalizations, newly diagnosed medical conditions, or visits to a medical facility with study site personnel. The memory aid is not a diary for the collection of reactogenicity. Please refer to the SRM and [Section 7.3](#) for additional details.
- Collect a blood sample (approximately 20 mL). Alternatively, for subjects who have consented to participate in the subset, collect approximately 100 mL of blood.
- Ask the parent(s)/legal guardian or the subject to contact the investigator immediately if any significant illness or hospitalization occurs.

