- Percentage of subjects with at least 1 AE occurring during the following time periods:
  - 30 Days after each vaccination
  - 30 Days after any vaccination
  - During the Stage 1 vaccination phase (from the first study vaccination [Visit 1] through 1 month after the second study vaccination [Visit 4])
- Percentage of subjects reporting at least 1 immediate AE after each vaccination.
- The number of days subjects missed school or work because of AEs during the Stage 1 vaccination phase (Visit 1 through Visit 4).

The following endpoints will be described after the booster vaccination in Groups 1 through 4:

- Percentage of subjects reporting local reactions (pain, redness, and swelling) and by severity within 7 days after the booster vaccination.
- Percentage of subjects reporting systemic events (fever, vomiting, diarrhea, headache, fatigue, chills, muscle pain other than muscle pain at any injection site, and joint pain) and by severity within 7 days after the booster vaccination.
- Percentage of subjects reporting the use of antipyretic medication within 7 days after the booster vaccination.
- Percentage of subjects with at least 1 SAE during the following time periods:
  - During the booster vaccination phase (from the booster vaccination [Visit 10] through 1 month after the booster vaccination [Visit 11])
  - During the booster follow-up phase (from 1 month after the booster vaccination [Visit 11] through 6 months after the booster vaccination [Visit 12])
  - From the booster vaccination (Visit 10) through 6 months after the booster vaccination (Visit 12)
- Percentage of subjects with at least 1 MAE occurring during the following time periods:
  - During the booster vaccination phase (from the booster vaccination [Visit 10] through 1 month after the booster vaccination [Visit 11])
  - During the booster follow-up phase (from 1 month after the booster vaccination [Visit 11] through 6 months after the booster vaccination [Visit 12])

- From the booster vaccination (Visit 10) through 6 months after the booster vaccination (Visit 12)
- Percentage of subjects with at least 1 NDCMC occurring during the following time periods:
  - During the booster vaccination phase (from the booster vaccination [Visit 10] through 1 month after the booster vaccination [Visit 11])
  - During the booster follow-up phase (from 1 month after the booster vaccination [Visit 11] through 6 months after the booster vaccination [Visit 12])

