  - From the booster vaccination (Visit 10) through 6 months after the booster vaccination (Visit 12)
- Percentage of subjects with at least 1 AE occurring during the following time periods:
  - During the booster vaccination phase (from the booster vaccination [Visit 10] through 1 month after the booster vaccination [Visit 11]).
- Percentage of subjects reporting at least 1 immediate AE after the booster vaccination.
- The number of days subjects missed school or work because of AEs after the booster vaccination.

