**Table 6. Analysis Intervals for AEs, SAEs, MAEs, and NDCMCs**

No.	Analysis Interval	Analysis Population	Interval Start Date (Inclusive)	Interval Stop Date (Inclusive)	Safety Data
1	Within 30 days of Vaccination 1	Vax 1 safety	Vax 1 date	Vax 1 date + 30 days	AE, SAE, MAE, NDCMC
2	Within 30 days of Vaccination 2	Vax 2 safety	Vax 2 date	Vax 2 date + 30 days	AE, SAE, MAE, NDCMC
3	Within 30 days of any Stage 1 vaccination	Safety	Vax 1 date or Vax 2 date	Vax 1 date +30 days or Vax 2 date +30 days	AE, SAE, MAE, NDCMC
4	During Stage 1 vaccination phase	Safety	Visit 1 date	Visit 4 date	AE, SAE, MAE, NDCMC
5	During Stage 1 follow-up phase	Follow-up Stage 1	Visit 4 date +1	Visit 5 date	SAE, MAE, NDCMC
6	Throughout Stage 1	Safety	Visit 1 date	Visit 5 date	SAE, MAE, NDCMC
7	During booster vaccination phase	Booster vax safety	Visit 10 date	Visit 11 date (or end of booster vaccination day)	AE, SAE, MAE, NDCMC
8	During booster vaccination follow-up phase	Follow-up booster	Visit 11 date + 1, or end of booster vaccination date + 1 for early withdrawal subjects	Visit 12 date	SAE, MAE, NDCMC
9	Throughout booster phase	Booster safety	Visit 10 date	Visit 12 date	SAE, MAE, NDCMC

Abbreviations: MAE = medically attended adverse event; NDCMC = newly diagnosed chronic medical condition; vax = vaccination.

Three analysis intervals will be applied to immediate AEs (Table 7).

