#### **6.2.2.3. Adverse Events**

Descriptive summary reports will be generated for AEs reported during the Stage 1 and booster vaccination phases (analysis intervals 1, 2, 3, 4, and 7 in [Table 6](#)) and will be similarly displayed as the summary output described in [Section 6.1.2.3](#).

The differences in subjects in each vaccine group (Group 1 – Group 3) reporting at least 1 AE during the Stage 1 vaccination phase may be summarized. The corresponding 95% CIs will also be computed using the Miettinen-Nurminen method.

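### Adverse events after the booster are counted over a visit-dependent 28 to 42 days, but after Vaccinations 1 and 2 over a fixed 30 days, so the descriptive per-dose percentages are not like for like

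*SAP*

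**What the plan says.** SAP Table 6 sets the intervals for AEs, serious AEs (SAEs), medically attended AEs (MAEs) and newly diagnosed chronic medical conditions (NDCMCs). Interval 1, "Within 30 days of Vaccination 1", stops at "Vax 1 date + 30 days". Interval 2 stops at "Vax 2 date + 30 days". Both ends are inclusive. The only short-term booster interval is number 7. It starts on the Visit 10 date and stops at "Visit 11 date (or end of booster vaccination day".

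The protocol fixes the timing of that visit in the heading of Section 6.3.5: "Visit 11 (28 to 42 Days After Visit 10), Postbooster Blood Draw".

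The endpoint lists in SAP 3.1.2 follow the same pattern. For Stage 1 the periods include "30 Days after each vaccination". For the booster the only period listed for AEs in general is "During the booster vaccination phase (from the booster vaccination [Visit 10] through 1 month after the booster vaccination [Visit 11". Protocol Section 2 agrees.

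SAP 6.2.2.3 puts these intervals into one set of outputs: "Descriptive summary reports will be generated for AEs reported during the Stage 1 and booster vaccination phases (analysis intervals 1, 2, 3, 4, and 7". SAP 6.1.2.3, which covers the primary safety endpoints, also refers to Table 6.

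**The concern.** The percentage of subjects with at least one AE depends on how long they are observed. For Vaccinations 1 and 2 the analysis window is a fixed number of days. For the booster it depends on when the clinic sees the subject. Booster safety is a primary safety endpoint, and a reader of the AE tables will naturally look along the row from Vaccination 1 to Vaccination 2 to booster. Part of any difference seen that way would reflect appointment timing.

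Elsewhere the SAP treats the three vaccinations alike. Table 7 uses 30 minutes for immediate AEs after each of them, and Table 8 uses the vaccination date plus 6 days for reactogenicity. Table 6 departs from that pattern without a stated reason. Its interval 4 is also bounded by visits, but it spans both primary doses (173 + 28 = 201 to 194 + 42 = 236 days), so it is not a per-dose counterpart to interval 7.

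**Working it through.** The plan states no AE rate, and no power or sample size depends on these intervals, so there is no figure of its own to reproduce.

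**Inputs**
- Intervals 1 and 2: 30 days elapsed, 31 calendar days inclusive (SAP Table 6).
- Interval 7: Visit 10 to Visit 11, with Visit 11 on day 28 to 42 (SAP Table 6, Protocol 6.3.5).
- Assumed, because the documents are silent: a 30-day AE rate p of 5% to 30%, and Visit 11 spread evenly over its 15 permitted days.

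**Step 1: window length.** With Visit 11 on day d, interval 7 covers d + 1 calendar days, against 31.
- Day 28: 29/31 = 0.94 (shorter)
- Day 29: 30/31 = 0.97 (shorter)
- Day 30: 31/31 = 1.00 (equal)
- Day 35: 36/31 = 1.16 (longer)
- Day 42: 43/31 = 1.39 (longer)

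With an even spread, 2/15 = 13% of subjects have a shorter window, 1/15 = 7% an equal one and 12/15 = 80% a longer one. The mean Visit 11 day is 35.

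**Step 2: effect on the percentage, constant hazard.** P(d) = 1 − (1 − p)^((d + 1)/31). For p = 10% and d = 28, this is 1 − 0.9^(29/31) = 9.39%.

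| p | Day 28 | Day 35 | Day 42 | Mean over days 28–42 | Mean excess (points) |
|---|---|---|---|---|---|
| 5% | 4.69% | 5.78% | 6.87% | 5.78% | +0.8 |
| 10% | 9.39% | 11.52% | 13.60% | 11.51% | +1.5 |
| 20% | 18.84% | 22.83% | 26.62% | 22.79% | +2.8 |
| 30% | 28.37% | 33.91% | 39.03% | 33.83% | +3.8 |

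**Step 3: the same with a front-loaded hazard.** Half of the 31-day hazard falls in the first 7 days and half is even over the other 24: P(d) = 1 − (1 − p)^(0.5 + 0.5(d + 1 − 7)/24).

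| p | Day 28 | Day 35 | Day 42 | Mean over days 28–42 | Mean excess (points) |
|---|---|---|---|---|---|
| 5% | 4.80% | 5.51% | 6.21% | 5.51% | +0.5 |
| 10% | 9.60% | 10.98% | 12.34% | 10.98% | +1.0 |
| 20% | 19.25% | 21.84% | 24.34% | 21.82% | +1.8 |
| 30% | 28.95% | 32.55% | 35.97% | 32.52% | +2.5 |

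A day-28 visit lowers the figure slightly in every row. The day-42 column would need every subject to attend on the last permitted day.

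**Step 4: what a 30-day booster window would cover.** SAP Table 5 ends collection of plain nonserious AEs at Visit 11, so coverage is min(30, d) days. With an even spread the mean is (28 + 29 + 13 × 30)/15 = 29.8 days. Vaccination 2 has the same limit, because Stage 1 collection ends at Visit 4, which is 28 to 42 days after Visit 3. The booster and Vaccination 2 would therefore match in both definition and coverage. Collection of SAEs, MAEs and NDCMCs resumes at Visit 12 for the time since Visit 11, so those lose nothing.

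**The case against.** The strongest defence is that the SAP carries out the protocol as written. The booster AE endpoint is defined as Visit 10 through Visit 11, and that matches the collection period. The safety objectives are descriptive. The only safety differences specified are Group 1 minus Group 3, described for Stage 1 (SAP 5.2.1.3 and 6.2.2.1 to 6.2.2.4), and SAP 5.2.1.3 says the safety intervals are not for testing hypotheses. All four groups share the same booster rule. A common window would also leave other differences between the doses: Stage 2 is open-label, the booster comes about four years after Vaccination 2, and only about 394 of 1590 subjects enter Stage 2.

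All of that stands. There is no mismatch between protocol and SAP, and no planned comparison is biased. It does not make the unequal window useful, though. The window is the one difference that existing data can remove. Natural pairings also remain: by Protocol Table 3, Groups 1 and 3 receive the same single product at Vaccination 2 and at the booster, and Groups 2 and 4 receive the same two products at Vaccination 1 and at the booster.

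A reader might infer more than the documents support:
- *That the booster is longer-exposed by construction.* It is not. Visits on days 28 and 29 give a shorter window and day 30 an equal one. The bracketed alternative stop date, read with the early-withdrawal wording in interval 8, suggests that some intervals may end without a Visit 11. Longer on average is likely, but it depends on actual visit dates.
- *That Vaccination 2 has a fully fixed exposure.* For plain nonserious AEs it does not, because collection stops at Visit 4.

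**Conclusion.** The booster AE percentages cover 28 to 42 days, depending on scheduling, and those for Vaccinations 1 and 2 cover 30. Set side by side, they are not like for like. On the assumptions above, the booster figure is higher on average by 0.8 to 3.8 points (constant hazard) or 0.5 to 2.5 points (front-loaded). If visits cluster at days 28 to 30 the effect vanishes or reverses slightly, and if they cluster late it grows. The consequence is confined to descriptive reading across doses. The primary immunogenicity tests and the planned group comparisons do not change. This is an inexpensive improvement to a primary safety summary and does not correct an error.

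**What to change.** Add one row to SAP Table 6:
- Interval: within 30 days of booster vaccination
- Start: booster date
- Stop: booster date + 30 days
- Population: booster vaccination safety
- Data: AE, SAE, MAE, NDCMC

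Report it beside intervals 1 and 2. Keep interval 7 as the protocol-defined booster phase, so no endpoint definition changes. In interval 7, define the alternative stop date given in brackets and state which subjects it applies to. Align its wording with the early-withdrawal rule in interval 8.

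The cost is one extra descriptive table from data already collected. For subjects seen on day 28 or 29, the last 2 days or 1 day of plain nonserious AE collection are missing. A footnote should say so and note that Vaccination 2 has the same limit at Visit 4.

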**Table 7. Analysis Intervals for Immediate AEs**

No.	Analysis Interval	Analysis Population	Interval Start Date/Time (Inclusive)	Interval Stop Date/Time (Inclusive)
1	Vaccination 1	Vax 1 safety	Vax 1 time	Vax 1 time + 30 minutes
2	Vaccination 2	Vax 2 safety	Vax 2 time	Vax 2 time + 30 minutes
3	Booster vaccination	Booster vax safety	Booster vax time	Booster vax time +30 minutes

Abbreviation: vax = vaccination.

### 3.5.2. Reactogenicity Data

The reactogenicity data collected from the study e-diary will include local reactions (redness, swelling, and pain at the injection site) and systemic events (fever, vomiting, diarrhea, headache, fatigue, chills, muscle pain other than muscle pain at the injection site, and joint pain) and use of antipyretic medication.

Reactogenicity data will be recorded in the e-diary from the day of each vaccination (Day 1), following investigational product administration, to Day 7. Local reactions will be collected only for the left arm, which is the MenABCWY or bivalent rLP2086 injection site. See Table 8.

**Table 8. Analysis Interval for Reactogenicity Data**

No.	Analysis Interval	Analysis Population	Interval Start Date (Inclusive)	Interval Stop Date (Inclusive)
1	Vaccination 1	Vax 1 safety	Vax 1 date	Vax 1 date + 6 days (or until resolved day)
2	Vaccination 2	Vax 2 safety	Vax 2 date	Vax 2 date + 6 days (or until resolved day)
3	Any Stage 1 Vaccination	Safety	Vax 1 or Vax 2 date	Vax 1 or Vax 2 + 6 days (or until resolved day)
4	Booster Vaccination	Booster safety	Booster vax date	Booster vax + 6 days (or until resolved day)

Abbreviation: vax = vaccination.

#### 3.5.2.1. Local Reactions Endpoints

##### Local Reaction Presence (Proportion of Subjects Reporting Each Local Reaction)

For each local reaction, the derivation of whether or not the specific reaction occurred on each day and “any day (Days 1 to 7)” will be made. The variable will be calculated for each vaccination as well as overall reactions for any vaccination. The derivation of this variable is given in Table 9 below.

**Table 9. Derived Variables for Local Reactions**

Variable	Yes (1) a	No (0) b	Missing (.)
Each day (Days 1 to 7)	Subject/parent/legal guardian reports the reaction as “mild,” “moderate,” or “severe” on each individual day.	Subject/parent/legal guardian reports the reaction as “none” on the individual day.	Subject/parent/legal guardian did not report on the reaction on the individual day.
Any day (Days 1 to 7)	Subject/parent/legal guardian reports the reaction as “mild,” “moderate,” or “severe” on any Day 1-7.	Subject/parent legal guardian reports the reaction as “none” on all 7 days or as a combination of “none” and missing on all 7 days.	Subject/parent/legal guardian did not report on the reaction on any of the 7 days.

- a. For redness and swelling, “mild,” “moderate,” or “severe” categories are based on the caliper size reported in the e-diary and as defined in Table 10.
- b. For redness and swelling, “none” means 0 to 4 caliper units reported in the e-diary.

A caliper (measuring device) is used to measure the redness or swelling of the injection site area. Caliper units (range: 1-21+) are converted to cm, with 1 caliper unit equal to 0.5 cm, then categorized as none, mild, moderate, or severe based on the grading scale in Table 10. Pain at the injection site will be assessed by the subject/parent/legal guardian according to the grading scale in Table 11.

**Table 10. Grading of Redness and Swelling at Injection Site**

None	0 to 2.0 cm (0 to 4 caliper units)
Mild	>2.0 to 5.0 cm (5 to 10 caliper units)
Moderate	>5.0 to 10.0 cm (11 to 20 caliper units)
Severe	>10.0 cm (>20 caliper units)

**Table 11. Grading of Pain at Injection Site**

None	No pain
Mild	Does not interfere with activity
Moderate	Interferes with activity
Severe	Prevents daily activity

### Maximum Severity for Local Reaction

The maximum severity (highest grading) of each local reaction within 7 days of vaccination will be derived for each vaccination as well as any vaccination. The maximum severity will be derived as follows:

- = ., if values are missing for all Days 1-7;
- = 0, if the subject/parent/legal guardian reports all reactions as ‘none’ or a combination of missing and ‘none’ for all Days 1-7;
- = *highest grade* (maximum severity) within 7 days of vaccination, if the answer is not ‘none’ for at least 1 day.

### Duration of Each Local Reaction

For subjects experiencing any local reactions (or those with derived reactions as defined in [Table 9](#)), the maximum duration (last day of reaction – first day of reaction +1) will be derived for the study vaccination. Resolution of the event is the last day on which the event is recorded in the e-diary or the date the event ends if it is unresolved during the subject diary-recording period (end date collected on the CRF), unless chronicity is established. If there is no known end date, the duration will be considered unknown and set to missing.

For reactions that continue into the next vaccination visit, the duration will be calculated in a segmented fashion. The reaction end date will be set to the day prior to the next vaccination and will have a new start date as the day of next vaccination and duration will be calculated separately from this start date to the date of resolution. Subjects with reactions spanning multiple vaccination visits will be included in a footnote.

Subjects with no reported reaction have no duration.

In summary, the following variables will be derived for local reactions:

1. Each local reaction on each day (Days 1 to 7) after each vaccination.
2. Each local reaction on any day (Days 1 to 7) after each vaccination and any vaccination.
3. Any local reaction on any day (Days 1 to 7) after each vaccination and after any vaccination.
4. Maximum severity of each local reaction on any day (Days 1 to 7) after each vaccination and any vaccination.
5. Maximum duration of each local reaction after each vaccination.

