7.3. Safety

Any subject who receives at least 1 dose of investigational product will be included in the evaluation for safety. The following safety parameters will be assessed as described in the Study Procedures section ([Section 6](#)) and [Schedule of Activities](#):

- Physical examination.
- Reactogenicity: solicited local reactions and systemic events, including fever.
- Use of antipyretic medication.
- Unsolicited AEs and SAEs.

A medical history will be obtained and a physical examination will be performed on all subjects at Visit 1 to establish a baseline, and at Visit 10 prior to the booster vaccination. When taking the medical history and performing the physical examination, particular care must be taken to note any neuroinflammatory and autoimmune conditions, such as transverse myelitis, uveitis, optic neuritis, and multiple sclerosis. Significant medical history and observations from the physical examination will be documented on the CRF. In addition, a urine pregnancy test will be performed on all female subjects.

The safety parameters include reactogenicity, ie, both local reactions and systemic events that occur in the 7 days (Days 1 to 7) after investigational product administration. These prompted e-diary events are:

- Local reactions at the site of investigational product administration (redness, swelling, and pain).
- Systemic events (fever, vomiting, diarrhea, headache, fatigue, chills, muscle pain other than muscle pain at the injection site, and joint pain).

Local reactions, systemic events, and use of antipyretic medication associated with vaccine administration will be collected using an e-diary. For events that resolve after Day 7, the end date will be collected in the symptoms resolved date CRF. If a subject does not complete the e-diary for 7 days, end dates of local reactions, systemic events, or antipyretic medication use that were ongoing on the last day the e-diary was completed by the subject will be collected on the symptoms resolved date CRF.

Immediate AEs, defined as AEs occurring within the first 30 minutes after investigational product administration, will be assessed and documented on the AE CRF. The time of onset will be recorded for any AEs that occur on the same day as investigational product administration.

Medically attended AEs and newly diagnosed chronic medical conditions will also be assessed throughout the study and documented on the appropriate AE CRF. A medically

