7.4. Electronic Diary

An e-diary will be issued based on a personal digital assistant or equivalent technology, and used to monitor and record the subject's local reactions, systemic events, and use of antipyretic medication for 7 days after each vaccination. Grading scales for local reactions and systemic events are based on US FDA Guidance for Industry, Toxicity Grading Scale for Healthy Adult and Adolescent Volunteers Enrolled in Preventive Vaccine Clinical Trials.⁴² The e-diary allows recording of these assessments only within a fixed time-window, thus providing the accurate representation of the subject's experience at that time.

For local reactions and systemic events that resolve after Day 7, the end date will be collected on the CRF. If the e-diary is not completed for 7 days, the end dates of local reactions, systemic events, or antipyretic medication use that occurred during the 7 days will be collected on the CRF. The investigator or designee should contact the parent(s)/legal guardian or subject in order to obtain stop dates for any solicited reactions or other solicited data ongoing on the last day that the e-diary was completed.

Data reported on the e-diary will be transferred electronically to the e-diary vendor (a trusted third party), where they will be available for review by investigators at all times via an Internet-based portal. At intervals agreed upon between the vendor and Pfizer, these data will be transferred electronically into Pfizer's database for analysis and reporting. These data do not need to be reported by the investigator on the CRF.

Investigators will be required to review the e-diary data online at frequent intervals to evaluate subject compliance and as part of the ongoing safety review.

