##### **3.1.2. Primary Safety Endpoints**

The following endpoints will be described after Vaccinations 1 and 2 in the bivalent rLP2086 arms (Group 2 and 4 subjects) combined.

- Percentage of subjects reporting local reactions (pain, redness, and swelling) and by severity within 7 days after each vaccination visit.
- Percentage of subjects reporting systemic events (fever, vomiting, diarrhea, headache, fatigue, chills, muscle pain other than muscle pain at any injection site, and joint pain) and by severity within 7 days after each vaccination visit.
- Percentage of subjects reporting the use of antipyretic medications within 7 days after each vaccination visit.

- Percentage of subjects with at least 1 SAE during the following time periods:
  - 30 Days after each vaccination
  - 30 Days after any vaccination
  - During the Stage 1 vaccination phase (from the first study vaccination [Visit 1] through 1 month after the second study vaccination [Visit 4])
  - During the Stage 1 follow-up phase (from 1 month after the second study vaccination [Visit 4] through 6 months after the second study vaccination [Visit 5])
  - Throughout Stage 1 (from the first study vaccination [Visit 1] through 6 months after the second study vaccination [Visit 5])
  
- Percentage of subjects with at least 1 MAE occurring during the following time periods:
  - 30 Days after each vaccination
  - 30 Days after any vaccination
  - During the Stage 1 vaccination phase (from the first study vaccination [Visit 1] through 1 month after the second study vaccination [Visit 4])
  - During the Stage 1 follow-up phase (from 1 month after the second study vaccination [Visit 4] through 6 months after the second study vaccination [Visit 5])
  - Throughout Stage 1 (from the first study vaccination [Visit 1] through 6 months after the second study vaccination [Visit 5])
  
- Percentage of subjects with at least 1 NDCMC occurring during the following time periods:
  - 30 Days after each vaccination
  - 30 Days after any vaccination
  - During the Stage 1 vaccination phase (from the first study vaccination [Visit 1] through 1 month after the second study vaccination [Visit 4])
  - During the Stage 1 follow-up phase (from 1 month after the second study vaccination [Visit 4] through 6 months after the second study vaccination [Visit 5])
  - Throughout Stage 1 (from the first study vaccination [Visit 1] through 6 months after the second study vaccination [Visit 5])

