#### **6.1.2.1. Local Reactions and Systemic Events**

The derived variables for the presence of each local reaction, each systemic event, any local reaction, and any systemic event occurring within 7 days following each vaccination will be summarized.

The presence and maximum severity of each reaction/event and any reaction/event within 7 days (over all Days 1 to 7) after each vaccination and any vaccination will be summarized through proportions of subjects, percentages, and associated 95% Clopper-Pearson CIs.

For each local reaction and systemic event, the maximum duration of each reaction/event will be descriptively summarized for each vaccination. Only subjects experiencing the reaction/event will be included in the analysis.

Use of antipyretic medication will also be displayed by the number of subjects and percentage who used antipyretic medication on each day and any day after each vaccination and any vaccination. Maximum duration of use will also be summarized by vaccination.

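### Solicited reactions with no known end date drop out of the duration summary, which can understate its maximum and upper tail

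*SAP*

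**What the plan says.** Diary recording is short: "Reactogenicity data will be recorded in the e-diary from the day of each vaccination (Day 1), following investigational product administration, to Day 7" (SAP 3.5.2). Under SAP 3.5.2.1, duration is the last day of the reaction minus the first day, plus 1. The last day is the last one recorded in the diary or, failing resolution there, "the date the event ends if it is unresolved during the subject diary-recording period (end date collected on the CRF), unless chronicity is established". The closing step is "If there is no known end date, the duration will be considered unknown and set to missing". SAP 3.5.2.2 derives the systemic-event variables in a similar way.

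The protocol supports this with follow-up. Section 7.3 states: "For events that resolve after Day 7, the end date will be collected in the symptoms resolved date CRF". Section 7.4 adds: "The investigator or designee should contact the parent(s)/legal guardian or subject in order to obtain stop dates for any solicited reactions".

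In the analysis, "the maximum duration of each reaction/event will be descriptively summarized for each vaccination" and "Only subjects experiencing the reaction/event will be included in the analysis" (SAP 6.1.2.1). SAP 5.2 makes n, mean, median, SD, minimum and maximum the default statistics. SAP 5.3.2.1 plans no sensitivity analysis for reactogenicity data. Its statement that little is missing rests on diary entries that cannot be skipped; it does not address end dates.

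**The concern.** An end date found in a completed diary is never unknown. It is normally unknown only when the reaction was still present at the last diary entry and no later date was obtained, or when the reaction became chronic. Missingness is therefore related to the quantity being summarised. For each such reaction the plan knows that the duration is at least (last day known present − first day + 1), and it discards that bound.

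The chronic case deserves separate mention. SAP 3.5.2.1 excepts chronic reactions from the CRF end-date route and gives them no other duration. Read literally they have no end date and become missing, and no amount of follow-up changes that.

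At stake is the descriptive picture of how long reactions last after each vaccination, including the booster. The maximum is printed by default, so deleting one persistent reaction can lower it. The booster groups are small (about 132 in each of Groups 1 and 3, and about 65 in each of Groups 2 and 4; SAP 2.2.1), so a single subject can decide the maximum.

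**Working it through.** The plan states no duration and no share of unknown end dates, so there is no figure to reproduce. The check has two parts.

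**1. Which reactions the rule reaches**

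| Situation | What the documents provide | Duration |
|---|---|---|
| Ends within a completed diary | Diary | Known |
| Ongoing at the last diary entry, end date obtained | CRF | Known, at its true length |
| Runs into the next vaccination | Cut at the day before, restarted, footnoted (SAP 3.5.2.1) | Kept, in segments |
| Ongoing at the last diary entry, no end date obtained | Nothing | Missing |
| Chronicity established | No rule stated | Missing on a literal reading |

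Only the last two rows are affected. In the third row the plan already uses a cut-off with a footnote rather than deletion.

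**2. Possible size (all inputs assumed)**

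Let μ be the true mean duration, p the share of reactions lasting more than 7 days, m the mean duration among those, and u the fraction of those with no end date.

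- Reported mean = (μ − u·p·m) / (1 − u·p)
- Reported share above 7 days = p(1 − u) / (1 − u·p)

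For a geometric distribution, p = (1 − 1/μ)^7 and m = 7 + μ. With μ = 3, p = (2/3)^7 = 0.0585 and m = 10. At u = 10% the reported mean is (3 − 0.1 × 0.0585 × 10) / (1 − 0.1 × 0.0585) = 2.9415 / 0.99415 = 2.96 days.

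The mixture is 95% geometric with mean 2.5 days and 5% geometric with mean 14 days, so μ = 0.95 × 2.5 + 0.05 × 14 = 3.075.

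| Assumed distribution | p | True mean | Mean, u = 10% | Mean, u = 50% | Mean, u = 100% |
|---|---|---|---|---|---|
| Geometric, mean 2 | 0.78% | 2.00 | 1.99 | 1.97 | 1.94 |
| Geometric, mean 3 | 5.85% | 3.00 | 2.96 | 2.79 | 2.56 |
| Geometric, mean 4 | 13.35% | 4.00 | 3.91 | 3.50 | 2.92 |
| Mixture | 5.64% | 3.075 | 3.00 | 2.71 | 2.33 |

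- **Mean:** it falls in every case. At u = 10% the largest fall is 4.00 − 3.91 = 0.09 day.
- **Median:** it changes in one cell only (geometric mean 4, u = 100%, from 3 to 2 days).
- **Upper tail:** for geometric mean 3, the reported share above 7 days goes from 5.85% to 5.30% (u = 10%), 3.01% (u = 50%) and 0% (u = 100%).

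Not every unknown is a long reaction. Suppose diaries stop on Day 3 and 10% of reactions lasting 3 days or more are lost. With geometric mean 3, (2/3)² = 44.4% last that long, with mean 2 + 3 = 5 days. The reported mean is (3 − 0.1 × 0.444 × 5) / (1 − 0.0444) = 2.91 days, and the share above 7 days becomes 5.51%. The direction is still downward. The known minimum here is only 3 days or less, though, so these values must be treated as censored and not averaged as if they were complete durations.

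**The case against.** The strongest reply is that recovery of end dates is well organised. Sites review the diary online, contact subjects for stop dates (Protocol 6.2.1, 6.2.3, 6.3.4, 7.4), enter them on a dedicated CRF (Protocol 7.3), and follow up ongoing reactogenicity at Visits 2, 4 and 11, which fall 28 to 42 days after each dose. Redness or swelling beyond the caliper's range is reported daily until it is back within range (Protocol 7.4.1.1). When this works, long reactions stay in the table at their true length, and the maximum may already come from one of them. This stands. A reader might infer that the rule strips out the longest reactions as a class, or that the reported durations are necessarily biased. The documents support neither: the rule reaches only what follow-up leaves unknown, plus chronic cases, and that share is not given.

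A second reply is that the loss is visible. The n in the duration table can be subtracted from the number with the reaction, and affected reactions remain in the reactogenicity listing (SAP 6.7.1). This stands in part: subtraction gives a count but not how long those reactions had lasted. Table shells and programming rules are separate documents (SAP 2) and may already show such a count; the SAP does not require it.

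A third reply is that setting an unknown value to missing is a prespecified choice that avoids imputation. That is fair against imputing an end date. It is weaker against a censored value, which uses only what was observed.

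**Conclusion.** This is a minor reporting gap. The rule can drop persistent reactions from the duration summary and can push its maximum and upper tail downward. The effect on the mean and median is probably small: under the assumed distributions, less than 0.1 day and nil when up to 10% of reactions longer than 7 days are unknown. The actual size cannot be determined from the documents. The direction rests on unknown end dates arising mainly from reactions still present at the last entry, which follows from how the end date is derived.

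Since duration is reported under the heading of primary safety endpoints, a reader might infer that those endpoints are affected. They are not. The listed endpoint for local reactions is "Percentage of subjects reporting local reactions (pain, redness, and swelling) and by severity within 7 days after each vaccination visit" (SAP 3.1.2); duration is not in the lists in SAP 3.1.2 or 3.2.2. Presence and maximum severity are taken from Days 1 to 7 and need no end date. The immunogenicity hypothesis test does not use these data.

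**What to change.** Amend SAP 3.5.2.1, with the same rule for systemic events, so that for each reaction, vaccination and group:

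- the number of reactions with unknown end date is reported, with chronic cases included and identified;
- the known minimum duration (last day known present − first day + 1) is kept as a right-censored value and is not averaged as if it were complete;
- the maximum is printed as '≥ x days' when a censored value is the largest;
- a reaction known to be present on Day 7 with no end date counts as lasting to at least Day 7, which is at least 7 days if it began on Day 1.

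A Kaplan-Meier median is optional and a matter of preference. SAP 3.5.2.2 indicates that Stage 1 has already been reported, so the practical target is the Stage 2 booster tables, with a footnote to the Stage 1 tables if any durations there were set to missing.

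The cost is one SAP sentence and an extra row per table, with no new data collection. The downside is slightly less simple duration tables. If the count is zero, the row shows it.
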